2. SPECIFIC AIMS

Primary Aim: Conduct a pilot randomized clinical trial testing two implementation interventions designed to support delivery of ACHIEVE-D at community-based psychiatric rehabilitation programs.

H1.1. Both the standard and enhanced interventions will increase knowledge of and self-efficacy to deliver ACHIEVE-D, and result in high-fidelity delivery of ACHIEVE-D.

H1.2 Compared to the standard intervention, the enhanced version will lead to greater knowledge, self-efficacy, and ACHIEVE-D fidelity.

Secondary Aims:

1. Assess the acceptability, appropriateness, and feasibility of the adapted ACHIEVE curriculum to coaches, peer leaders, program directors and other staff.
2. Assess consumer outcomes of self-reported diet and physical activity, weight, attendance and satisfaction.

This study will lead to a refined intervention that will contribute to the future development of a certified ACHIEVE-D training program for mental health staff and peers, and thus facilitate future widespread dissemination of an evidence-based behavioral weight-loss program for individuals with SMI.

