4. DESIGN SUMMARY

The core design is a randomized, two-arm, parallel, pilot clinical trial where 10 psychiatric rehabilitation program sites will be randomized to a 6-month standard or enhanced intervention. This trial will recruit and enroll participants at each site – staff, peer leaders, and mental health consumers, (Figure 1). The primary outcome variables will be coaches' knowledge, self-efficacy, and fidelity to the ACHIEVE curriculum.

Figure 1. Study Populations with Corresponding Activities and Outcomes for Each Site

We estimate up to 280 mental health organization staff and peer leaders will participate in data collection including program directors, coaches, and other psychiatric rehabilitation program staff. Two coaches and one peer leader per study site will be randomized to the standard or enhanced intervention. Up to 120 mental health consumers across all sites will be enrolled, and all will receive group weight-management sessions delivered by the trained coaches at their site.

The ACHIEVE-D curriculum is designed to fit into and will be part of the regular psychiatric rehabilitation programming that is already being conducted.

Randomized groups:

Standard intervention: At those sites assigned to the standard group, two staff and one peer will receive training and approximately 8-12 consumers with SMI will participate in the ACHIEVE weight loss program. The standard intervention will combine onboarding training, ongoing online training, and online avatar-assisted motivational interviewing practice^{19,20} for all coaches, as well as organizational strategy meetings to garner the leadership support for ACHIEVE implementation²¹.

Enhanced intervention: At those sites assigned to the enhanced group, the implementation intervention will include all standard strategies and will add performance coaching for the coaches.

Trainings and meetings will be remote during the COVID-19 pandemic.

We outline the eligibility criteria sites in Section 5. Then, we describe the eligibility criteria as well as data collection and measurements for each study population separately in Sections 6-8.

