10. RANDOMIZATION AND BLINDING

Following baseline data collection, sites will be randomized to the standard or enhanced arms. Randomized blocks of 2 in random order will be used to create the randomization sequence. The random sequence and allocation groupings will be stored in RedCap, only the data analyst will distinguish the treatment assignment to sites. Due to the nature of the intervention, both participants and interventionists will be aware of the assignment. Data collectors measure study outcomes. Investigators, staff and participants are masked to outcome data, with the exception of trial statistician, study coordinator, data analyst and independent study monitor.

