13. DATA ANALYSIS

We will assess the effects of the implementation intervention on providers' knowledge self-efficacy, and fidelity to the ACHIEVE curriculum, as well as consumer outcomes using generalized linear mixed-effects models under the intent-to-treat approach. Mean models will include a binary intervention group indicator, time indicators, intervention by time interaction terms, and fixed effects for the 10 study sites. The time indicator coefficients estimate time-specific mean outcome changes in the "standard" group and interaction coefficients estimate the between-arm differences of time-specific outcome changes from baseline. The linear combination of these time-specific coefficients captures the time-specific mean outcome changes in the "enhanced" group. The model will use an unstructured variance covariance matrix for the repeated outcome measurements over time within individuals. To assess whether knowledge and self-efficacy mediate implementation intervention

effects, we will estimate the magnitude of attenuation on intervention effects in the consumer outcome models with vs. without these measures. We will also examine potential moderators, e.g. study sites' implementation intervention fidelity and/or implementation climate, by adding appropriate interaction terms to the models. We will analyze survey data on our implementation measures prior to conducting focus groups in order to explore survey findings in depth (e.g., if providers' rate performance coaching as having mediocre acceptability, we will explore reasons why in the focus groups). We will use descriptive statistics to analyze survey measures of perceptions of acceptability, feasibility and appropriateness of implementation intervention and ACHIEVE-D. Point estimates and corresponding 95% confidence intervals will be obtained.

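### Sites are randomised, but the analysis model has no site-level error for arm effects, and no effect it names tests the fidelity part of H1.2

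*Combined protocol and SAP*

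**What the plan says.** Section 10 makes the site the unit of allocation: "Following baseline data collection, sites will be randomized to the standard or enhanced arms". Section 4 gives 10 sites, each with two coaches and roughly 8 to 12 consumers, and lists the primary outcomes as coaches' "knowledge, self-efficacy, and fidelity to the ACHIEVE curriculum". H1.2 in Section 2 is a superiority claim: "Compared to the standard intervention, the enhanced version will lead to greater knowledge, self-efficacy, and ACHIEVE-D fidelity".

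Section 13 analyses provider and consumer outcomes with "generalized linear mixed-effects models under the intent-to-treat approach". The mean model has a group indicator, time indicators, "intervention by time interaction terms, and fixed effects for the 10 study sites". The only covariance described is this: "The model will use an unstructured variance covariance matrix for the repeated outcome measurements over time within individuals". The between-arm effect is defined as a change: "interaction coefficients estimate the between-arm differences of time-specific outcome changes from baseline". The other effects interpreted (the time coefficients and their linear combination for the enhanced arm) are also changes. The consumer arm effects are used again for mediation: "we will estimate the magnitude of attenuation on intervention effects in the consumer outcome models with vs. without these measures".

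Table 2 (Section 6.2) marks both ACHIEVE fidelity forms only during follow-up, with no baseline. Section 6.3 takes fidelity from recordings of delivered sessions and from coach documentation on the same days. Section 11.2 sets a minimum of recordings in months 1, 3 and 6.

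**The concern.** When sites are randomised, the arm comparison is judged against variation between sites. Section 13 specifies no random site-by-time effect, no cluster-robust variance and no site-level degrees of freedom. The term mixed-effects leaves room for a random site effect, but none is stated, and a random site intercept beside fixed site effects would add nothing.

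For fidelity the difficulty comes before the error term. With no baseline, the question in H1.2 is a difference in level, while every effect Section 13 interprets is a change. An analyst following the text would report interactions that can be zero when performance coaching works. An analyst who builds the level contrast from the same model would get an interval that is too narrow if sites differ.

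For outcomes with a baseline, fixed site effects remove stable site differences but not differences between sites in how much people change. That matters most for consumer outcomes. They are secondary, but their arm effects feed the mediation analysis.

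**Working it through.** **Inputs.** 10 sites, taken as 5 per arm (Sections 4 and 10); 2 coaches and 8 to 12 consumers per site (Section 4); recordings at months 1, 3 and 6 (Section 11.2); 95% intervals (Section 13). The documents give no alpha, power, SD or ICC, so there is no stated figure to reproduce. ICCs are assumed and shown over a range. All rates are for a two-sided 5% test; interval coverage is 100% minus the rate.

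**Step 1: what can be estimated for fidelity.** The group indicator is the sum of five site indicators, so the mean model is always one short of full rank.

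| Recordings per coach | Columns | Rank |
|---|---|---|
| 1 | 11 | 10 |
| 3 | 15 | 14 |
| 6 | 21 | 20 |

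The group coefficient alone is not estimable. With two or more recordings the interactions are estimable, but they contrast later recordings with the first, which is after randomisation. The difference between the average of the site means in each arm is also estimable, but Section 13 does not name it. Adding 1 SD to enhanced sites at every recording (100 data sets, months 1, 3, 6) raised the t statistic for that level contrast by 3.2 on average and left the interaction t statistic unchanged (below 1e-6).

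**Step 2: error of the fidelity level contrast under the stated model.** With fixed site effects the error comes from coaches within sites, on 10 × (2 − 1) = 10 degrees of freedom. Take total variance 1, site share ρ and one score per coach. A site mean has true variance ρ + (1 − ρ)/2, but the model uses (1 − ρ)/2. The ratio is (1 + ρ)/(1 − ρ), and the true error rate is P(|t10| > 2.228/√ratio).

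- ρ = 0.10: ratio 1.1/0.9 = 1.222; 2.228/1.106 = 2.015; 7.1%.
- ρ = 0.20: ratio 1.2/0.8 = 1.5; 2.228/1.225 = 1.819; 9.9%.

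Simulation (400,000 trials per cell) gave 4.9%, 7.1% and 9.8% at ρ = 0, 0.10 and 0.20. Fitting the stated model to recordings at months 1, 3 and 6 (6,000 REML fits per cell, remaining variance split equally between coach and residual) gave 4.7%, 8.0% and 12.0% for the average over recordings, and 5.1%, 7.2% and 9.7% at month 6.

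**Step 3: outcomes with a baseline.** With two time points the fixed site effects cancel from the change scores. With m people per site and ICC of change ρ, the variance is understated by about DEFF = 1 + (m − 1)ρ, and the error rate is about 2[1 − Φ(1.96/√DEFF)]. For example, m = 12 and ρ = 0.05 give DEFF = 1 + 11 × 0.05 = 1.55; 1.96/1.245 = 1.574; 11.5%.

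| Outcome | m | ICC of change | DEFF | Approximation | Simulated |
|---|---|---|---|---|---|
| Coach knowledge, self-efficacy | 2 | 0.05 / 0.10 / 0.20 | 1.05 / 1.10 / 1.20 | 5.6 / 6.2 / 7.4% | 5.5 / 6.2 / 7.4% |
| Consumers | 8 | 0.02 / 0.05 / 0.10 | 1.14 / 1.35 / 1.70 | 6.6 / 9.2 / 13.3% | 6.6 / 9.2 / 13.5% |
| Consumers | 12 | 0.02 / 0.05 / 0.10 | 1.22 / 1.55 / 2.10 | 7.6 / 11.5 / 17.6% | 7.6 / 11.7 / 17.9% |

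**Step 4: the alternative.** A t-test on the 10 site means, with 10 − 2 = 8 degrees of freedom (critical value 2.306), held 5.0% to 5.1% in all 13 cells simulated.

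**The case against.** This is a pilot with no stated alpha or power. Every inflation figure rests on an assumed ICC, and the degrees of freedom used for the fidelity contrast are not in the plan. For knowledge and self-efficacy the effect is small; the large figures belong to secondary outcomes. All of that is true and limits the second fault. But H1.2 is worded as superiority, Section 13 promises 95% intervals, and intervals that are too narrow mislead whoever plans the next trial.

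Performance coaching is monthly, so its benefit may build. If a 1 SD difference is absent at month 1 and present at month 6, the month-6 interaction has an average t of 2.3 to 2.6 and is significant in 56% to 66% of simulated trials. The stated model is therefore not blind to every fidelity effect. It misses whatever is already present at the first recording, and growth after that recording is not what H1.2 claims.

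The aliasing is partly a matter of coding. If sites are nested in arm with sum-to-zero effects, the group coefficient becomes the level contrast. That repairs the target, but the contrast still carries within-site error.

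Finally, switching to site means when the site variance is estimated at zero would happen often (51% of trials with 2 coaches, 56% with 12 consumers, at ICC 0), and a site-mean change test drops participants without both measurements. This is a fair criticism of the switch. A model that allows a negative site variance avoids it.

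**Conclusion.** The concern holds and should be settled before any between-arm analysis. The fidelity fault needs no assumption about clustering: none of the effects named in Section 13 measures a difference in fidelity level. The missing site-level error is a fault of specification whatever the ICC; its consequences depend on the ICC. They are nil at zero, small for coach knowledge and self-efficacy, moderate for a fidelity level contrast, and largest for consumer outcomes (up to 17.9% at 12 per site and ICC 0.10). These rates assume 5 sites per arm, equal site sizes and complete data. If attendance and satisfaction are compared between arms with this model, they share the fidelity problem, because they have no baseline either; Section 13 does not say which consumer outcomes enter it.

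**What to change.** Amend Section 13 as follows.

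1. **Outcomes with a baseline.** Keep the fixed site effects if wanted, add a random site-by-time effect, and test arm-by-time on about 8 degrees of freedom. Participants with a missing 6-month value stay in, consistent with intent-to-treat.
2. **Fidelity, and any other outcome without a baseline that is compared between arms.** Name the arm difference in level as the target and say whether it is averaged over recordings or taken at month 6. Drop the fixed site effects. Use a random site effect, plus site-by-time for repeated recordings, on about 8 degrees of freedom, or a t-test on the 10 site-mean scores.
3. **Zero site variance.** Report the site-mean t-test as a check. Either allow the site variance to be negative in the model, or name the site-mean test in advance as primary when that variance is estimated at zero. With complete, equal-sized sites the unbounded model and the site-mean test coincide.

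Step 3 is needed because a site variance held at zero or above, tested on 8 degrees of freedom, is conservative: 1.7%, 2.5%, 3.5% and 4.3% at ICC 0, 0.02, 0.05 and 0.10 with 12 consumers, and 2.6% to 3.6% with 2 coaches at ICC 0 to 0.20. Its half-width with 12 consumers at ICC 0 is 0.46 SD, 26% wider than under the stated model.

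The cost is wording and a different model call; design, sample and data collection stay as they are. Expected half-widths without clustering, site-mean analysis against the stated model, are:

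- consumers at 12 per site: 0.41 against 0.36 SD of change (about 13% wider);
- coach change: 1.00 against 0.93 SD (8%);
- fidelity level: 1.00 against 0.97 SD (3%).

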6.2 Data collection procedures

Data collection is outlined in Table 2. Data collection for coaches and peer leaders will occur remotely via telephone or Zoom and/or online RedCap survey or delivered paper questionnaires. We will collect follow-up measures at 3 months and 6 months at completion of ACHIEVE curriculum.

Participant reimbursement for data collection for staff coach participants is estimated at \$160 total for completing all data collection. Participant reimbursement for data collection for peer leader participants includes \$75 for completing data collection, up to \$320 (\$20/hour) for participating in trainings and up to \$1500 (\$20/hour) per site for participating in delivery of the curriculum.

Table 2. Data Collection Schedule For Coaches and Peer Leaders

	Baseline	Follow-up		
		During	6M Post	6M Post project completion
Primary Outcomes				
ACHIEVE curriculum weight management knowledge	x		x	
ACHIEVE curriculum exercise knowledge	x		x	
Self-efficacy to deliver ACHIEVE curriculum	x		x	
ACHIEVE Fidelity Document Assessment Form		x		
ACHIEVE Fidelity Video Assessment Form		x		
Other Measures				
Demographics & prior training	x			
Attitudes towards individuals with obesity	x			
Calculated BMI	x		x	
CARDIA/EARLY Q – sedentary behavior	x		x	
Block Dietary Fat Q	x		x	
Block Dietary Fruit/Vegetable Q	x		x	
EARLY Eating Away from Home Q	x		x	
EARLY SSB Consumption Q	x		x	
Perceived Stress Scale	x		x	
Self-Efficacy recall			x	
Beliefs about Motivational Interviewing	x	x	x	
Importance and Confidence of Using MI	x	x	x	
Avatar MI Performance Measurements	x	x	x	
Avatar Motivational Interviewing (MI) satisfaction survey			x	
Perceived Usefulness (motivational interviewing avatar platform)			x	
Fidelity to Motivational Interviewing	x	x	x	
Implementation Measures				
Acceptability of training	x		x	
Feasibility of training	x		x	
Appropriateness of training	x		x	
Motivation for implementation	x		x	
Implementation Climate	x			
Qualitative Assessment				
Focus Group Interviews			x	x

Abbreviations: BMI – body mass index; Q – questionnaire; SSB – sugar-sweetened beverage.

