6.3 Measurements

Measurements for coaches and peer leaders will be conducted using standardized operating procedures and quality control methods. Specific study forms (RedCap or paper) will be used to collect data.

Primary Outcomes

Knowledge of the ACHIEVE curriculum. We will assess knowledge about key elements of the ACHIEVE curriculum using two measures: A 22-item *ACHIEVE Curriculum Weight Management Knowledge* measure and a 16-item *ACHIEVE Curriculum Exercise Knowledge* measure. The study team created these questions

using best practices recommended by the National Board of Medical Examiners for item writing⁵⁶. These measures will be assessed at baseline and 6 months.

Self-efficacy to deliver the ACHIEVE curriculum. We will assess self-efficacy to deliver key elements of the ACHIEVE curriculum, where participants rate their confidence to deliver each element on a 10-point scale. The study team used principles from other related self-efficacy measures in creating our measure^{57,58}. This measure will be assessed at baseline and 6 months. Given that this type of self-report measure may be subject to response shift bias^{59,60}, we will also have coaches reflect upon their baseline ability to carry out these elements at the 6-month point, which will enable us to determine whether response shift bias may be present.

Fidelity to the ACHIEVE curriculum (ACHIEVE fidelity video assessment form and ACHIEVE fidelity documentation assessment form). To determine fidelity to the curriculum, we will use two data sources. First, coaches will video-record two ACHIEVE group sessions each month at each site, one per coach. Two study team members will view each recording and use a rating tool to assess fidelity to key elements of the ACHIEVE curriculum. We will calculate inter-rater reliability between coders. Second, a study team member will examine documentation practices of the coaches on the same day that video tapes are obtained. The study team has identified elements from both data sources that will be summed to create a composite score. Numerical values from all items will be used. For Y/N items, 'Yes' will equal a numerical score of 2 and 'No' a numerical score of 1.

Other Measures

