11.3 Enhanced Intervention Group

The enhanced intervention includes all components of the standard intervention along with the addition of performance coaching. Performance coaching may be particularly beneficial when, as in the present case, the evidence-based practice is new to most implementers. Each month a master trainer on the study team will meet with the Coach to provide tailored feedback and performance coaching session. The feedback will be used to 1) promote curriculum fidelity; 2) facilitate motivational interviewing skill development; and 3) help coaches plan for improved ACHIEVE curriculum delivery.

12. DATA MANAGEMENT and SECURITY

Quantitative Data. Each participant will be assigned a unique study ID number for data collection, instead of name or other identifying information. The link between identifying information and the study ID will be kept in a separate database with password access available only to the data analyst, statistician and principal investigators. Study team members are trained to protect integrity and confidentiality of the data. Data will be published only in aggregate, with no identifying characteristics of individuals published or presented. We will store data in a Johns Hopkins REDCap database. REDCap data is housed on secure servers at the Johns Hopkins Biostatistics Center under firewall protection. Database access is password protected and restricted to authorized personnel only and REDCap provides audit trails for tracking data manipulation and user activity. Any paper records will be kept in locked file cabinets. Kognito, a health simulation company, developed the avatar simulations for this project and hosts the avatar training platform and dashboard. Avatar performance measurement data for motivational interviewing practice conversations is accessible only by the individual study participant (provider) and the study team, not shared outside Kognito. Kognito stores data securely behind two firewalls.

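### Section 13 lists a variable that arises after randomisation, sites' implementation intervention fidelity, as an effect moderator; arm effects conditional on it are not randomised comparisons

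*Combined protocol and SAP*

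**What the plan says.** Section 13 closes its account of the mixed models with a plan to examine, as potential moderators, sites' "implementation intervention fidelity and/or implementation climate, by adding appropriate interaction terms to the models". It does not define the fidelity variable, distinguish the two candidates by when they are measured, or add a caveat for either.

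The timing can be read from other sections:

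- Section 10: "Following baseline data collection, sites will be randomized to the standard or enhanced arms". Baseline measures therefore precede assignment, and anything observed during delivery follows it.
- Section 6.2, Table 2: the row "Implementation Climate" has a single mark, at baseline. Both ACHIEVE fidelity forms are marked only during the intervention.
- Section 6.3, on curriculum fidelity: "coaches will video-record two ACHIEVE group sessions each month at each site, one per coach".
- Section 11.3: "The enhanced intervention includes all components of the standard intervention along with the addition of performance coaching". On what that coaching is for: "The feedback will be used to 1) promote curriculum fidelity".
- Section 2, H1.2, relative to the standard intervention: "the enhanced version will lead to greater knowledge, self-efficacy, and ACHIEVE-D fidelity".

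Section 4 names curriculum fidelity as one of three primary outcomes. The documents give no effect size, power or error rate for the moderator analysis.

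**The concern.** A moderator analysis asks whether the arm effect differs between kinds of site. The answer keeps the protection of randomisation only if the kind of site was settled before assignment. Baseline climate meets that condition. Fidelity of delivery does not, because it is partly a result of what the site was assigned to.

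A model with an arm-by-fidelity interaction reports the arm effect at a given fidelity. That compares enhanced sites with standard sites that reached the same fidelity by a different route, so the two groups may differ in unmeasured ways such as organisational capacity. Where fidelity itself works on the outcome, holding it fixed also removes part of the effect the trial is looking for. In a pilot meant to refine the strategy, such a figure could be read as evidence about which sites benefit from coaching.

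**Working it through.** **1. Which variable is meant.** Two readings are open.

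- *Fidelity to the implementation strategy*, the more literal reading. It builds up over six months of training, avatar practice and leadership meetings. Performance coaching exists in one arm only, so once it is counted the score covers different content in each arm and equal scores do not mean equal things.
- *ACHIEVE curriculum fidelity.* It has no baseline value and is a primary outcome. It cannot moderate the model in which it is the outcome. In the consumer models it lies on the path the intervention is meant to act through.

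Both readings are post-randomisation.

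**2. What conditioning does.** The plan gives no figure to reproduce, so every value below is an assumption. Let A be arm (0 or 1) and U an unmeasured site factor with mean 0 and SD 1, independent of A by randomisation. Let F be fidelity, with SD 1 within arm, and Y the change in outcome from baseline:

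- F = aA + bU + error
- Y = tA + cU + dF + error

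The randomised effect of arm is t + ad. Given A and F, the expected value of U is b(F − aA), so

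- expected Y = (t − abc)A + (d + bc)F.

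The conditional arm effect is t − abc, which differs from the randomised effect by −a(d + bc). The difference is zero if a = 0, or if neither fidelity (d) nor the site factor behind it (bc) bears on change. The slope on F is the same in both arms, so the interaction coefficient is zero, as it should be.

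**3. Numbers, with t = 0.5 and d = 0.**

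| b | c | a = 0 | a = 0.5 | a = 1.0 |
|---|---|---|---|---|
| 0.5 | 0.5 | 0.50 | 0.5 − 0.125 = 0.375 | 0.5 − 0.25 = 0.25 |
| 0.3 | 0.6 | 0.50 | 0.5 − 0.09 = 0.41 | 0.5 − 0.18 = 0.32 |
| 0.6 | 0.6 | 0.50 | 0.5 − 0.18 = 0.32 | 0.5 − 0.36 = 0.14 |

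Simulated site-level change scores (5 sites per arm, residual SD 0.5) for the last two rows gave 0.41 and 0.31, then 0.32 and 0.14. Runs with 1,000 sites gave 0.41 and 0.32, then 0.32 and 0.14. The shift is therefore bias, not small-sample noise.

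**4. When a false interaction appears.** This needs a further condition: the arm must change how fidelity depends on U. Suppose coaching cuts the loading b to kb in the enhanced arm. The slopes on F become bc (standard) and kbc / (k²b² + 1 − b²) (enhanced). With k = 0.3 and c = 0.6:

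- b = 0.3: 0.054/0.918 − 0.18 = 0.059 − 0.18 = −0.12
- b = 0.6: 0.108/0.672 − 0.36 = 0.161 − 0.36 = −0.20

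The simulations gave −0.12 and about −0.19 to −0.21, with a true interaction of zero.

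**5. Baseline climate instead.** A pre-randomisation variable has a = 0 by design. In every simulated scenario with 10 sites the mean arm effect was 0.50 (0.496 to 0.504) and the mean interaction within about 0.01 of zero. The interaction estimate had an SD of about 0.7 to 0.76, larger than the assumed effect itself.

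**The case against.** The strongest reply has four parts.

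*The arm's effect on this variable is not documented.* Section 13 speaks separately of the implementation intervention and of fidelity to the ACHIEVE curriculum. H1.2 and the purpose given for coaching concern the latter. Delivery of the shared training components might be equal across arms, and with a = 0 and an unchanged link to site capacity there is no bias. This stands for the strategy reading, so H1.2 cannot be cited to show that the arm changes that variable. The variable is still measured after assignment, and it is still not comparable across arms if coaching enters the score.

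*The planned model gives some protection.* Section 13 includes fixed site effects and estimates differences in change from baseline. Stable site capacity that acts only on the level of the outcome is removed. This also stands: bias through U requires U to affect change. The protection does not extend to curriculum fidelity as an outcome, which has no baseline value.

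*False moderation is not shown.* A reader might infer that the analysis will produce interactions that do not exist. In the simple linear case it does not; step 4 shows the extra condition needed.

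*It is one exploratory line in a pilot.* The sentence says potential moderators, gives examples, and already names climate. A reader might go further and infer that the trial's main result is compromised. The documents do not support that, because the intent-to-treat arm comparison does not condition on fidelity. But fidelity is one of only two moderators named, and the and/or wording would allow it to be used alone.

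**Conclusion.** The point holds in limited form. Section 13 admits an undefined post-randomisation variable as a moderator, and arm effects conditional on it would not be randomised comparisons. They can be expected to be biased if the arm affects fidelity and if fidelity, or an unmeasured site factor that also drives it, affects change in the outcome. The first condition is what the protocol itself predicts on the curriculum reading and is open on the strategy reading. The second is plausible but not stated anywhere.

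No size can be derived from the documents. The values of about 0.37 and 0.25 against a true 0.5 illustrate the mechanism with loadings of 0.5 on both paths and capacity acting on change; the other rows show how far they move with the assumptions. It would be tempting to say that most of a real effect would be lost, but only the combination of strong loadings and a 1.0 SD shift (0.14) comes near that, and nothing in the protocol supports those values. This is a correction worth making to a secondary, exploratory analysis. The primary comparison is not affected.

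**What to change.** Amend the moderator sentence in Section 13 to say the following:

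- Moderators are limited to variables measured before randomisation: baseline implementation climate and, if wanted, the baseline values of motivation for implementation and prior training. Table 2 already schedules all three at baseline.
- Implementation intervention fidelity is defined, is not entered in interaction models, and is summarised descriptively by arm. Any association with outcomes is labelled exploratory and non-randomised.
- Moderator results are reported as exploratory, with confidence intervals.

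The cost is a short edit and the loss of one exploratory model; no new data are needed. The change removes the bias but does not make the analysis precise. With 10 sites, any site-level moderator estimate stays very imprecise. An association examined within the enhanced arm alone would rest on 5 sites and remain open to confounding by site capacity.
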